4.1 Description of the Study Design

Analytical Observational Study

In analytical observational studies, researchers try to establish an association between

exposure(s) and outcome(s) (10). Depending on the direction of inquiry, these studies can be directed forward, known as cohort studies, or backward known as case-control studies.

The VIOLA Study is an analytical study designed to quantify a relationship or association between two variables – an exposure and an outcome. The exposure, Melody®, is pre-determined for all participants to receive as opposed to experimental studies where an investigator assigns each participant to receive or not receive a particular exposure.

The VIOLA Study was designed to be directed forward using a cohort population at multiple study sites. A cohort is defined as a "group of people with a shared characteristic." In cohort studies, different groups of people with varying levels of exposure are followed over time to evaluate the occurrence of an outcome. Melody® does not have varying levels of exposure but is an overall new exposure for the population.

This observational study will not dictate the cancer screening regimens that the site clinicians and participants utilize. Instead, this study collects data on individuals' cancer screening practices, cancer outcomes, and other factors if needed. Because no regimens are dictated, the VIOLA Study can capture information about and evaluate various cancer screening practices, including the use of different tests or cancer screening regimens.

The association of exposure to outcome this study is attempting to define: How does the use of Melody® before mammography affect participation rates in breast cancer screening?

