4.2 Study Endpoints

4.2.1 Primary Endpoint

It is common knowledge that disparities exist in breast health, preventative care, and screening mammography. Namida Lab, Inc. knows the potential of Melody® to be a tool that bridges the gap between underserved populations and positive health outcomes. The administration of Melody® does not require additional appointments or trips and can be done by any member of a medical team.

As such, Namida Lab, Inc. is partnering with federally qualified health centers and large employers to evaluate the clinical utility of Melody®. Do women in populations with historically low compliance rates with screening mammography, who receive Melody® as the first step in the breast health continuum of care, participate in screening mammograms at higher rates than previous years?

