10.1 Statistical and Analytical Plans

An a priori power analysis was conducted using G*Power v3.1.9.2 to determine the minimum sample size required to find significance with a desired level of power set at 0.80 and alpha (a) level at 0.05. Based on this analysis, it was determined that a minimum of 205 participants were required to ensure adequate power for a Pearson's Chi-square Test of Independence. (12, 13, 14) (Appendix L)

Each participant will be required to take an enrollment survey that collects information on race, ethnicity, and socio-economic status. Participant's addresses will be obtained as part of the requisition process for the CLIA lab, from which information on geographic location can be obtained. In addition to the factors listed above, the enrollment survey also collects information on status and type of health insurance, reproductive health, breast health knowledge, prior screening history, and family and personal history of cancer.

The exit survey has been designed to collect information on the participant experience with Melody® and comprehension of the information Melody® relayed through their site clinician. In addition, information is collected on participant's intention to schedule/participate in future screening mammograms and/or change in intention to participate in a previously scheduled screening mammogram.

Data will be analyzed using SPSS Statistics software. To determine the presence of significant changes, Unpaired T-tests or Mann-Whitney U-test will be used with a significance level set at P < 0.05.

Due to the effect of COVID-19 on screening rates, screening mammogram participation rates will be compared to rates reported for the state of Arkansas in 2019.

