10.2 Statistical Hypothesis

Primary endpoint:

- H_0 = Participation rates in yearly screening mammography with the incorporation of Melody® (examined by geographic location, socio-economic status, race, and ethnicity) will not be greater than participation rates recorded in 2019.
- H_1 = Participation rates in yearly screening mammography with the incorporation of Melody® (examined by geographic location, socio-economic status, race, and ethnicity) will be greater than participation rates recorded in 2019.

Secondary endpoint:

- H_0 = Participation rates in yearly screening mammography, with the incorporation of Melody® (examined by clinical sites), will not be greater than participation rates recorded

in 2019.

- H_0 = Participation rates in yearly screening mammography, with the incorporation of Melody® (examined by clinical sites), will not greater than participation rates recorded in 2019.

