10.3 Analysis Datasets

Primary endpoint datasets will be broken down by classifications outlined in the table below.

Primary Endpoint Characteristic

Ethnicity	Hispanic
	Non-Hispanic
Race	American Indian-Alaska Native
	Asian
	Black or African American
	Native Hawaiian or Other Pacific Islander
	White
Socio-economic status	\$35,000 or less
	\$35,000-\$80,000
	\$80,000-\$130,000
	\$130,000-\$200,000
	\$200,000 or higher
Geographic Location	Metropolitan
	Nonmetropolitan

Analysis of secondary endpoint datasets will be analyzed by comparing screening mammography participation rates reported by the clinical site from 2019 to screening mammography participation rates observed after the study.

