10.4.2 Analysis of primary efficacy endpoints

Data for primary efficacy endpoints will be presented as follows:

Analysis of Primary Efficacy Endpoints

		VIOLA	2019	Total
Ethnicity	Hispanic	N (% of total for VIOLA)	N (% of total for 2019)	N (% of total)
	Non-Hispanic	N (% of total for VIOLA)	N (% of total for 2019)	N (% of total)

P value		P =?		
Race	American Indian-Alaska Native	N (% of total for VIOLA)	N (% of total for 2019)	N (% of total)
	Asian	N (% of total for VIOLA)	N (% of total for 2019)	N (% of total)
	Black or African American	N (% of total for VIOLA)	N (% of total for 2019)	N (% of total)
	Native Hawaiian or other Pacific Islander	N (% of total for VIOLA)	N (% of total for 2019)	N (% of total)
	White	N (% of total for VIOLA)	N (% of total for 2019)	N (% of total)
P value		P =?		
Socio-economic status	\$35,000 or less	N (% of total for VIOLA)	N (% of total for 2019)	N (% of total)
	\$35,000-\$80,000	N (% of total for VIOLA)	N (% of total for 2019)	N (% of total)
	\$80,000-\$130,000	N (% of total for VIOLA)	N (% of total for 2019)	N (% of total)
	\$130,000-\$200,000	N (% of total for VIOLA)	N (% of total for 2019)	N (% of total)
	\$200,000 or higher	N (% of total for VIOLA)	N (% of total for 2019)	N (% of total)
P value		P =?		
Geographic Location	Metropolitan	N (% of total for VIOLA)	N (% of total for 2019)	N (% of total)
	Nonmetropolitan	N (% of total for VIOLA)	N (% of total for 2019)	N (% of total)
P value		P =?		

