10.4.3 Analysis of the Secondary Endpoints

Analysis of the secondary endpoints will be presented as follows:

Analysis of Secondary Endpoints				
		VIOLA	2019	Total
Site 1	Followed through with screening mammogram	N (% of total for VIOLA)	N (% of total for 2019)	N (% of total)
	Did not follow through with screening mammogram	N (% of total for VIOLA)	N (% of total for 2019)	N (% of total)
P value		P =?		

The analysis will be conducted for each site enrolled in the VIOLA Study.

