The results of the power analysis can be found in Table 1 below. Remember that power analysis calculations using lower effect sizes will tell you that you need larger samples, but these are the calculations easiest to justify. The calculations in the H1 hypothesis (percentage difference in compliance between treated and untreated groups) are the initial power calculation. The second calculation under accounting for 10% drop-out, increases the sample size to account for the drop-out rate you requested. Based on the moderate effect size of $\Delta\% = 20\%$ with a power level of .80, we recommend you recruit 205 participants for this study split evenly between treatment and non-treated groups ($N = 103$ each).

Table 1
Minimum Sample Size Needed for Range of Effect Sizes for Each Study Hypothesis

Hypothesis	Power level	Effect Size			
		Effect	Low	Moderate	
H1: Compliance for Treatment vs Untreated groups	$\Delta\%$		10	20	30
Pearson's Chi-square test of Independence	.80	776	186	78	
	.85	886	214	88	
	.90	1038	248	104	
Accounting for 10% drop-out rate	$\Delta\%$		10	20	30
	.80	854	205	86	
	.85	975	235	97	
	.90	1142	273	114	
Minimum sample size	$\Delta\%$		10	20	30
	.80	854	205	86	
	.85	975	235	97	
	.90	1142	273	114	

Note. Alpha level = .05. The numbers represented here are the total number of participants that would be needed for the sample.

Write-up to include in a methods section (if needed)

An a priori power analysis was conducted using G*Power v3.1.9.2 to determine the minimum sample size required to find significance with a desired level of power set at .80, an alpha (α) level at .05. Based on this analysis, it was determined that a minimum of 205 participants (two groups of 103) were required to ensure adequate power for a Pearson's Chi-square Test of Independence. (Cohen, 1988; Erdfelder, Faul, & Buchner, 1996; Faul, Erdfelder, Lang, & Buchner, 2007).

References

Cohen, J. (1988). Statistical power analysis for the behavioral sciences (2nd ed.). Hillsdale, NJ: Lawrence Erlbaum Associates.

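### With no concurrent control, the primary conclusion appears to rest on the statewide Arkansas 2019 rate, while the closer reference, each site's own 2019 rate, is planned only for the secondary endpoint

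*Protocol*

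**What the plan says.** Protocol 4.1 describes a forward-looking observational cohort without an untreated group: "The exposure, Melody®, is pre-determined for all participants to receive". The primary question in 4.2.1 is whether women in groups with poor past uptake "participate in screening mammograms at higher rates than previous years".

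The primary alternative hypothesis in 10.2 is that participation, "examined by geographic location, socio-economic status, race, and ethnicity) will be greater than participation rates recorded in 2019". It does not say whose 2019 rates these are. The only general statement of the source is in 10.1: "screening mammogram participation rates will be compared to rates reported for the state of Arkansas in 2019". The reason given there is the effect of COVID-19 on screening.

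The sites' own history appears in 10.3 for the secondary endpoint, which is analysed by "comparing screening mammography participation rates reported by the clinical site from 2019 to screening mammography participation rates observed after the study". The table in 10.4.3 sets this out site by site, with a row labelled "Followed through with screening mammogram" and its complement. The primary table in 10.4.2 sets VIOLA against 2019 by ethnicity, race, income and location. It has no overall row.

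Appendix L sized the study for a different layout, with participants "split evenly between treatment and non-treated groups".

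**The concern.** With no concurrent control, any difference between the enrolled women and the reference population that was there before Melody goes straight into the result. COVID-19 explains the choice of 2019 but not the choice of a whole state.

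Three features of the protocol make such a difference possible:
- Section 5.3 allows sites anywhere in the United States and recruits from clinics, employers and the general public.
- Sections 5.1 and 5.2 contain no criterion on past screening.
- Item 1 of the exit survey (Appendix J) recognises that some women may already have had a mammogram booked when they enrolled.

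The difference could run either way. Women from clinics with poor uptake may start below the state rate. Volunteers, or women already booked, may start above it.

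The Protocol Summary presents the link between Melody and participation as the evidence needed for adoption into the standard of care. A misattributed difference would therefore matter.

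**Working it through.** **Which reference applies to the primary hypothesis.** Section 10.2 says only 2019. Section 10.1 names Arkansas 2019 without tying it to an endpoint. Sections 10.3 and 10.4.3 give site 2019 rates to the secondary endpoint. No third source is named. Arkansas is therefore the likeliest primary reference, by elimination.

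**Reproducing the plan's own figure.** Appendix L inputs: proportions 0.50 and 0.70, two-sided alpha 0.05, power 0.80, equal groups. With mean proportion 0.60:

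n per group = [1.960 × √(2 × 0.60 × 0.40) + 0.8416 × √(0.50 × 0.50 + 0.70 × 0.30)]² / 0.20² = (1.358 + 0.571)² / 0.04 ≈ 93.

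The total is 186, and 186 × 1.10 = 204.6, rounded to 205. Both figures agree with Appendix L. They size a treated group against an untreated group, which the design in 4.1 does not have.

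**Sensitivity to a gap (illustration).** Assumptions, none of them an Arkansas or site figure:
- The reference rate is 50%, borrowed from Appendix L.
- There is one overall comparison of 93 with 93.
- The gap is the rate the enrolled women would show without Melody, taken as equal to their own 2019 rate, minus the reference rate.
- The gap sizes are chosen for illustration.

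Let x and y be the counts with a mammogram in the reference and VIOLA groups, and p̄ = (x + y)/186. Then z = (y/93 − x/93) / √[2p̄(1 − p̄)/93]. A gain is declared when z > 1.96, the upper side of the two-sided test. Binomial probabilities are summed over all such (x, y).

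No Melody effect, reference 0.50:
- gap 0, VIOLA rate 0.50: gain declared 0.024
- gap +5, VIOLA rate 0.55: 0.097
- gap +10, VIOLA rate 0.60: 0.269

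True effect of 20 points, reference 0.50:
- gap 0, VIOLA rate 0.70: 0.799 (Appendix L reports 0.800)
- gap −5, VIOLA rate 0.65: 0.537
- gap −10, VIOLA rate 0.60: 0.269

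**What a better reference could recover.** If the reference equalled the women's own rate, the 20-point effect would be declared 0.799, 0.781 and 0.778 of the time at own rates of 0.50, 0.45 and 0.40. That is a best case. A site's 2019 rate describes the site's patients, not the women who volunteered. If site rates closed only half of a 10-point shortfall, 5 points would remain and the chance would be close to the gap −5 line above.

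**The case against.** Several points on the other side have force.

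- **The Arkansas sentence is general.** A reader might infer that 10.1 expressly makes the state rate the primary reference. It does not; this is the likeliest reading, and it should be put as one.
- **The percentages are not error rates of the planned analysis.** A reader might take 27% as VIOLA's false-positive rate. The documents do not support that: 10.4.2 has no overall comparison, 10.1 and 10.4.1 name t-tests or Mann-Whitney tests, and the 50% reference is assumed.
- **Site rates are historical too.** A reader might infer that switching to them restores 78% to 80% power. That needs the site rate to equal the volunteers' own prior rate, and no site rate is given. If volunteers are more often already booked than the site's 2019 patients were, the same bias remains.
- **The subgroup rows carry the sponsor's question.** Sections 3.1 and 10.2 are built on disparities by location, socio-economic status, race and ethnicity. Replacing those rows would go further than the problem requires. They may also remove part of a population difference, though only one factor at a time in the tables shown.
- **The protocol already claims only an association** (4.1) and collects screening history. Adjustment for it may be set out in an analysis plan that is not at hand.
- **Geography is a possibility.** Section 5.3 permits sites outside Arkansas but does not list any.

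These points limit the size of the claim and the reach of the remedy. They leave standing that a statewide rate does not measure change from previous years in the women studied, and that a closer reference is already planned but used only for the secondary endpoint.

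**Conclusion.** The point holds as a recommended improvement. The reference for the primary hypothesis is not clearly named. On the likeliest reading it is the Arkansas 2019 rate, which does not match the question in 4.2.1. A pre-existing difference could look like a Melody effect or mask one.

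The documents do not support saying which way the bias runs or how large it is, because they give no Arkansas, site or booking rate. Under the assumed 50% reference and a hypothetical 93 v 93 test, a 5-point gap moves a false gain from 2% to 10% in one direction, and the chance of finding a true 20-point effect from 80% to 54% in the other. A 10-point gap moves both figures to 27%. Site rates reduce the problem only as far as a site's 2019 patients resemble its volunteers.

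**What to change.** In 10.1 to 10.4:
1. Name the reference for the primary hypothesis.
2. Add one overall comparison, in the layout of 10.4.3, of completed screening mammograms in VIOLA with the participating sites' own 2019 rates. Weight the site rates by each site's VIOLA enrolment. Restrict them to ages 40 to 74 and to the same outcome window where records allow. Count the sampling error of both rates.
3. Use this comparison for the claim about change from previous years.
4. Keep the ethnicity, race, income and location rows. State that their comparison with Arkansas 2019 is context and does not by itself support a claim of a Melody effect.
5. Report completed mammograms by prior appointment (Appendix J, item 1) and by time since the last mammogram (Appendix D, Section 3, item 5), because selection and existing bookings can bias the result under either reference.
6. State the result as an association.

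The cost is modest. Site 2019 rates and the follow-through layout are already planned, and both survey items are already collected. The additions are one hypothesis, one table row, and a request to sites for age-restricted rates and a matching window. There are downsides: site rates may be less precise than a state rate and may lack subgroup breakdowns. Employer or general-public recruits may have no 2019 denominator and should be shown separately.

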10.2 Statistical Hypothesis

Primary endpoint:

- H_0 = Participation rates in yearly screening mammography with the incorporation of Melody® (examined by geographic location, socio-economic status, race, and ethnicity) will not be greater than participation rates recorded in 2019.
- H_1 = Participation rates in yearly screening mammography with the incorporation of Melody® (examined by geographic location, socio-economic status, race, and ethnicity) will be greater than participation rates recorded in 2019.

Secondary endpoint:

- H_0 = Participation rates in yearly screening mammography, with the incorporation of Melody® (examined by clinical sites), will not be greater than participation rates recorded

in 2019.

- H_0 = Participation rates in yearly screening mammography, with the incorporation of Melody® (examined by clinical sites), will not greater than participation rates recorded in 2019.

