- US Code of Federal Regulations applicable to clinical studies (45 CFR 46)
- ICH GCP E6
- Completion of Human Subjects Protection Training

Protocol Summary

Title: Validating Individualized breast cancer screening by Offering a new Link in Access

Short Title: The VIOLA Study

Précis: The VIOLA Study is a Clinical Utility Study to investigate the useability of Melody®, a tear-based screening assay for breast cancer developed and validated by Namida Lab, Inc., a high complexity CLIA certified lab.

The VIOLA Study will have multiple study sites, with a minimum participation of 205 women who are 40 to 74 years of age, at average risk for developing breast cancer, asymptomatic, and have no concerns or breast abnormalities.

Melody® consists of two parts: tear sample collection and clinical lab assay. Participants will have a tear sample collected at a study site. The clinical lab assay, Melody®, will be performed at Namida Lab, Inc. The results of the Melody® assay will be returned to the site clinician to be discussed with the participant.

Objectives: Primary Objective: Investigate the clinical utility of Melody® in federally qualified health centers in populations with historically low compliance rates with screening mammography.

Secondary Objective: Assess how incorporating Melody® into a primary care provider setting affects participation and confidence in the current breast health continuum of care.

Endpoint: Primary endpoint: The VIOLA Study is designed to quantify the relationship between two variables: an exposure and an outcome, by utilizing different study sites and recruiting from a diverse population.

Secondary endpoint: Quantifying the relationship between Melody® and increased participation in breast health care offers the clinical utility evidence required for adoption into the Standard of Care.

Population: Women ages 40-74 years old, at average risk for developing breast cancer

Number of Sites: 3+ sites

Study Agent: Melody® is a tear-based, high complexity lab-developed test. Melody® has been developed, validated, and will only be run by Namida Lab, Inc. as a tool in breast cancer screening.

Study Duration: 6-12 months

Participant Duration: Six months

Schematic of Study Design

The VIOLA Study: Validating Individualized breast cancer screening by Offering a new Link in Access

Define – Month 1-6 Study Design/Site Enrollment

- Recruit and consent study sites
- Establish study site principal investigator and study agreement consent

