3.2 Secondary Objective

Currently, Melody® is not intended to replace screening mammograms but an additional tool to facilitate more discussions between providers and patients. Tear sample collection can be done during any routine office visit and does not require specially trained personnel. The accessible collection allows patients to be tested in a clinic environment they are already familiar with by personnel they already know and trust. The goal for early iterations of Melody® is one more piece of clinical information gathered, leading to additional conversations about breast health, which may be the key to increased participation in annual or bi-annual screening mammograms.

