5.1 Participant Inclusion Criteria

To be eligible to participate in this study, an individual must meet all the following criteria:

- Female
- 40 to 74 years old
- Able to undergo the informed consent process
- Willingness to comply with all study procedures
- Available for the duration of the study
- In good general health and at average risk for developing breast cancer

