 Contraceptive Patch
 Intrauterine device (IUD)
 Vaginal Ring
 None
2. Are you currently using any hormone replacement therapy? (select one)
 Yes No
3. Please select what hormones you are currently taking: (select all that apply)
 Testosterone
 Estrogen
 Progesterone
 Other: _____
4. Hormone replacement medication name if known: _____
5. At what age did your periods begin? _____ (number)
6. Do you still have regular periods? (select one)
 Yes No
7. If you Do Not have regular periods, please select one of the following reasons: (select one)
 Menopause
 Hysterectomy
 Response to Birth Control
 Uterine Ablation
 Other (please describe): _____
 Unknown
8. Do you still have ovaries? (select one)
 Yes No

Section 3: Breast health:

1. Have you ever been told you have dense breast tissue? (select one)
 Yes No
2. Are you currently on, or have you been told, you should be on a high-risk breast cancer screening protocol? (select one)
 Yes No

3. Do you get an annual mammogram for breast cancer screening? (select one)
 Yes No
4. Do you get a bi-annual, every two years, mammogram for breast cancer screening? (select one)
 Yes No
5. When was your last screening mammogram? (enter date or select one)
(mm/dd/yyyy) ____/____/____ Unknown N/A
6. Have you ever received an abnormal screening mammogram? (select one)
 Yes No
7. From your last mammogram, what BI-RADS assessment category was on your mammogram results report? (select one)
 0 - Incomplete - Additional imaging evaluation and comparison to prior mammograms are needed.
 1 - Negative
 2 - Benign (non-cancerous findings)
 3 - Probably benign finding (follow-up in a short time frame is suggested)
 4 - Suspicious abnormality (biopsy should be considered)
 4A - Finding with a low likelihood of being cancer (more than 2% but no more than 10%)
 4B - Finding with a moderate likelihood of being cancer (more than 10% but no more than 50%)
 4C - Finding with a high likelihood of being cancer (more than 50% but less than 95%), but not as high as Category 5
 5 - Highly suggestive of malignancy (appropriate action should be taken)
 6 - Known biopsy-proven malignancy (appropriate action should be taken)
 Unknown

Section 4: Personal history and family history of cancer:

1. Please list below any cancers you have or have had in your lifetime.

No personal history of cancer Personal history unknown

Cancer Type	Year of diagnosis	Treatment	Treatment ongoing

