The first section of this report provides a basic conceptual understanding of power analyses and the elements in it that are used to calculate sample size. This will be followed with a discussion of the power analysis for your study. Table 1 presents a breakdown of the required minimum sample size at each power level for each effect size by hypothesis. The minimum sample needed at each power and effect level in the table is summarized at the bottom. The last section provides a breakdown of the screenshots of the power analyses at each power level at the moderate effect size so you can see how the sample size was calculated.

Understanding Effect and Sample Sizes

It is important to understand that the number attributed to a moderate effect size varies depending on the type of analysis used (e.g., correlation, regression, etc.). For example, when the research design calls for the use of an analysis of variance (ANOVA) model, a moderate effect size would be .25 measured as f (though partial eta-squared is another common measure, η^2_p). However, if the design requires the use of a multiple linear regression, a moderate effect size would be .15, measured as f^2 . We provide low, moderate, and high effect sizes when calculating power analyses so that you can look at the minimum sample sizes needed and choose appropriately.

It is typically best for the researcher to attempt to achieve the sample size recommended by power analysis calculations using the low or moderate effect size because this will require a larger sample, which will give you a higher probability of detecting a true effect. As a practical matter, however, when the researcher does not have the resources to achieve a sample size this large, the moderate or upper-moderate effect size may still provide guidance on choosing a more modest sample size (or if previous research suggests that a larger effect is possible).

Your Power Analysis

The type of analysis best suited for your research is *Pearson's Chi-square Test of Independence* analysis. The associated percent change effect size was used for a low effect ($\Delta\% = .10$), moderate ($\Delta\% = .20$), and high ($\Delta\% = .30$) effect sizes to conduct the *a priori* power analysis. The alpha level was set at .05. The power levels were set at both .80, .85, and .90 for comparison. The power analysis was conducted using G*Power v3.1.9.2.

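### Section 10 tests a yearly mammography rate over six-month participation without saying how women not due for screening are counted, although their last-mammogram date is collected

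*Protocol*

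**What the plan says.** The primary hypotheses in Protocol Section 10.2 concern "Participation rates in yearly screening mammography with the incorporation of Melody", compared with rates recorded in 2019. Section 10.1 names the Arkansas 2019 rate as the comparator and gives no look-back period for it.

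The Protocol Summary gives "Participant Duration: Six months". The only health and risk criterion in Section 5.1 is "In good general health and at average risk for developing breast cancer"; nothing in Sections 5.1 or 5.2 concerns being due, overdue or recently screened. Section 3.2 speaks of the discussion about Melody, "which may be the key to increased participation in annual or bi-annual screening mammograms", and Appendix K item 14 asks providers about two-yearly recommendations.

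The enrolment survey (Appendix D, Section 3) asks "Do you get a bi-annual, every two years, mammogram for breast cancer screening" and "When was your last screening mammogram". Section 10.1 mentions prior screening history as something collected, but Sections 10.3 and 10.4 give it no role. The table shell in Section 10.4.3 has two outcome rows per site, for women who did and did not follow through with a mammogram. The primary shell in Section 10.4.2 has subgroup counts and no outcome rows.

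**The concern.** A woman screened shortly before enrolment, or in the off year of a two-yearly schedule, may have no mammogram due during her six months. She follows her guideline, yet the Section 10.4.3 table offers her only two rows, and without an early mammogram she lands among those who did not follow through. For her, the outcome largely records her position in the screening cycle.

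If the comparator covers a longer period than the VIOLA window, such women lower the VIOLA rate more than the 2019 rate, and an effect in due or overdue women is diluted. Under-screened women are the ones the primary objective is about. Crediting a mammogram from the previous 12 months would place the recent screeners, but it would then count mammograms done before Melody. Either way a stated rule is needed, and Section 10 has none.

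**Working it through.** **Inputs from the documents (Appendix L).** Reference rate 0.50, rate with Melody 0.70, two-sided test, "The alpha level was set at .05", equal groups, 10% dropout, and the recommendation "with a power level of .80, we recommend you recruit 205 participants for this study".

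**Reproducing the plan's figure.** With a pooled-variance test of two proportions, 0.50 against 0.70 at power 0.80 needs 93 per group, 186 in total. Inflation: 186 × 1.10 = 204.6, rounded to 205. Both match Appendix L.

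**Share of adherent women due within six months.** Assume due dates are spread evenly over the cycle.
- Yearly screeners: 6/12 = 50% due.
- Two-yearly screeners: 6/24 = 25% due.

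If only due women were screened, these would be the ceilings for fully adherent women. Both lie below the planned 70%.

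**Dilution.** Let q be the share of enrolled women not due in the window. It is not in the documents, so a range is shown. Further assumptions: 70% of due women are screened, no not-due woman is, and the reference stays at 0.50 (a comparator covering a year or more).

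Observed rate p = 0.70 × (1 − q).

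Power to show an increase, with n = 93 per group and m = (p + 0.50)/2, is Φ{[(p − 0.50) − 1.96 × √(2m(1 − m)/n)] / √([p(1 − p) + 0.25]/n)}.

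For q = 0.10: p = 0.63 and m = 0.565. The null standard error is 0.0727 and the alternative one 0.0721. So (0.13 − 0.1425)/0.0721 = −0.173, and Φ = 0.43.

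| q | Observed rate | Power, 93 per group | Total N for 80% |
|---|---|---|---|
| 0 | 0.70 | 0.80 | 186 |
| 0.10 | 0.63 | 0.43 | 456 |
| 0.20 | 0.56 | 0.13 | 2172 |
| 0.286 | 0.50 | 0.025 | no gain left |
| 0.40 | 0.42 | about 0.001 | below reference |

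The gain vanishes where 0.70 × (1 − q) = 0.50, so q = 1 − 0.50/0.70 = 0.286.

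**Sensitivity to the layout.** Every VIOLA participant receives Melody and the comparator is a reported rate. If 186 women were tested against a fixed 0.50, power would be 0.95 at q = 0.10 and 0.37 at q = 0.20. The observed rates and the 0.286 break-even do not change.

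**Sensitivity to early screening.** Section 2.3.1 gives a false-positive rate of 46%. Assume that share of not-due women receives a High result and 70% of those are screened. At q = 0.286 the rate becomes 0.50 + 0.286 × 0.46 × 0.70 = 0.50 + 0.092 = about 0.59. That leaves roughly 9 of the planned 20 points.

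**The case against.** The strongest objection is that the protocol never writes a counting rule. It states no look-back, no due rule and no outcome window. Six months is how long a woman takes part; Section 10.3 refers to rates observed after the study, and Appendix J item 11 asks permission for later contact about a planned mammogram. The two outcome rows belong to the secondary, per-site table only. This stands: the misclassification is what the table implies as drawn, and the finding is the missing rule.

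A reader might infer that not-due women are non-participants whatever Melody does. The documents do not support that. The results script in Section 7.3.3 recommends a screening mammogram with no reference to the last one, and the sample report in Appendix I says scores above 0.1 should be referred for imaging. Some not-due women can be screened and counted.

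A reader might also infer that the bias would survive equal follow-up. An all-women 2019 rate over an equal window would contain not-due women too. Bias would then need a different not-due share in VIOLA, which nothing in the protocol shows. Likewise, a site compared with its own 2019 rate is distorted only if its window, guideline or recruitment mix differs between the two periods.

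Finally, the not-due shares are assumed, and populations with historically low compliance may contain fewer recent screeners. Recruitment also reaches large employers and the general public (Section 5.3), so the share need not be small. A derivation could sit in a separate analysis plan, but Section 10 already fixes the hypotheses, datasets and table shells, and it is there that yearly meets six months and accepted two-yearly screening.

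**Conclusion.** The point holds in a limited form. Participation is not tied to being due, to a look-back, or to a window matched to the 2019 rate, and the survey items needed to derive due status have no stated use in the analysis. An adherent woman not due has no correct row in Section 10.4.3.

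The size is conditional. With a comparator covering a year or more, 70% uptake in due women, none in not-due women and a 50% reference, 10% not due cuts the expected gain from 20 points to 13, 20% cuts it to 6, and about 29% removes it. On Appendix L's two-group layout, power falls from 0.80 to about 0.43 and 0.13 at the first two shares. Early screening of not-due women makes the loss smaller. The 50% is a planning input, not the Arkansas rate. Since the look-back of that rate is not given, a reader should not conclude that the result will be biased downward, or by how much. The change is worth making because it is cheap and removes an ambiguity that could matter a good deal.

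**What to change.** 1. In Section 10.3, derive due status at enrolment from Appendix D, Section 3, items 3 to 5 and the screening interval each site follows.
2. In the Section 10.4.3 table, give women not due in the window their own row. Report the rate among due or overdue women beside the all-women rate. Keep women with unknown dates as due, and add a check that excludes them.
3. For each site comparison, use the due-only rate as the main result only where the site can supply its 2019 rate on the same basis.
4. For the primary comparison, keep an all-women rate, because the published Arkansas figure cannot be restricted to due women. Count VIOLA mammograms over the same look-back or window as that figure, and give the due-only rate as a supporting analysis.
5. In Section 10.2, replace yearly with the interval actually observed.

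The cost is protocol wording, one derived variable and a modest data request to sites. Strata become smaller, and some last-mammogram dates will be unknown. Matching the window in step 4 may mean recording mammograms beyond six months if the Arkansas rate covers a longer period.
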